6.2. Exclusion Criteria

Participants are excluded from the study if any of the following criteria apply:

MEDICAL CONDITIONS

1. History or presence of or current cardiovascular, respiratory, hepatic, renal, gastrointestinal, endocrine, hematological, or neurological disorders capable of significantly altering the absorption, metabolism, or elimination of drugs; constituting a risk when taking the study treatment; or interfering with the interpretation of data.
2. History of herpes zoster (shingles) reactivation.
3. Evidence of active or latent tuberculosis (TB) as documented by medical history and examination, chest x-rays (posterior anterior and lateral), and TB testing: either a positive tuberculin skin test (TST; defined as a skin induration >5 mm at 48 to 72 hours, regardless of Bacillus Calmette-Guerin (BCG) or other vaccination history) or a positive (not indeterminate) QuantiFERON-TB Gold test.

NOTE: The choice to perform a TST or a QuantiFERON-TB Gold test will be made by the investigator according to local licensing and standard of care. The QuantiFERON-TB Gold test can only be used in countries where it is licensed, and the use of this test is dependent on previous treatment(s). This test may not be suitable if previous treatment(s) produced significant immunosuppression.
4. Alanine transaminase (ALT) >1.5x upper limit of normal (ULN).
5. Bilirubin >1.5xULN (isolated bilirubin >1.5xULN is acceptable if bilirubin is fractionated and direct bilirubin <35%).

MEDICAL CONDITIONS

6. Current or chronic history of liver disease, or known hepatic or biliary abnormalities (with the exception of Gilbert's syndrome or asymptomatic gallstones)

7. QTc >450 msec

NOTES:

- The QTc is the QT interval corrected for heart rate according to Bazett's formula (QTcB), Fridericia's formula (QTcF), and/or another method, machine-read or manually over-read.
- The specific formula that will be used to determine eligibility and discontinuation for an individual subject should be determined prior to initiation of the study. In other words, several different formulae cannot be used to calculate the QTc for an individual subject and then the lowest QTc value used to include or discontinue the subject from the trial.
- For purposes of data analysis, QTcB, QTcF, another QT correction formula, or a composite of available values of QTc will be used as specified in the Reporting and Analysis Plan (RAP).

8. History of serious or recurrent infections or has had an active infection within 14 days of receiving study medication.

9. History of diagnosis of obstructive sleep apnoea or significant respiratory disorder. Childhood asthma that has fully resolved is permitted.

10. Part A: History of active SIB within the past 6 months or any history of attempted suicide in a participant's lifetime.

11. History of current evidence of febrile seizures, epilepsy, convulsions, significant head injury, or other significant neurologic conditions.

PRIOR/CONCOMITANT THERAPY

12. Past or intended use of over-the-counter or prescription medication, including herbal medications, within 7 days (or 14 days if the drug is a potential enzyme inducer) or 5 half-lives (whichever is the longest) prior to dosing. Specific medications listed in Section 7.6 may be allowed.

13. Subject received a vaccine (either live attenuated or now-live) within 30 days prior to randomization, or plans to receive a live attenuated vaccine within 30 days + 5 half-lives (32 days) of the last dose of study medication.

PRIOR/CONCURRENT CLINICAL STUDY EXPERIENCE

14. Participation in the study would result in loss of blood or blood products in excess of 500 mL within a 56-day period.

15. Exposure to more than 4 new chemical entities within 12 months prior to the first dosing day.

16. The subject has participated in a clinical trial and has received an investigational

product within the following time period prior to the first dosing day in the current study: 30 days, 5 half-lives or twice the duration of the biological effect of the investigational product (whichever is longer).

DIAGNOSTIC ASSESSMENTS

17. Presence of Hepatitis B surface antigen (HBsAg) at screening Positive Hepatitis C antibody test result at screening.
18. Positive pre-study drug/alcohol screen.
19. Positive human immunodeficiency virus (HIV1 and 2) antibody test.
20. Regular use of known drugs of abuse.
21. Subjects with impaired renal function defined as Chronic Kidney Disease Epidemiology Collaboration (CKS-EPI) Creatinine > 1.6mg/dL with an age appropriate GFR ≤ 60 (mL/min/1.73 m²) estimated by the Chronic Kidney Disease Epidemiology Collaboration (CKD-EPI) equation [[Snyder, 2009](#) and [Levey, 2010](#)].
22. An elevated C-reactive protein (CRP) outside of the normal reference range.

OTHER EXCLUSIONS

23. Regular alcohol consumption within 6 months prior to the study defined as:
 - For UK - an average weekly intake of >14 units for males and females. One unit is equivalent to 8 g of alcohol: a half-pint (~240 mL) of beer, 1 glass (125 mL) of wine or 1 (25 mL) measure of spirits.
24. Cotinine or carbon monoxide levels indicative of smoking or history or regular use of tobacco- or nicotine-containing products within 6 months prior to screening.
25. Sensitivity to any of the study treatments, or components thereof, or drug or other allergy that, in the opinion of the investigator or medical monitor, contraindicates participation in the study
26. Unwilling or unable to swallow multiple size 00 capsules as part of study participation.

PART B SPECIFIC CRITERIA

27. History of SIB as measured using the C-SSRS or a history of attempted suicide.
28. A positive anti-nuclear antibody (ANA) outside of the normal reference range.
29. Fasting total cholesterol ≥ 300 mg/dL or triglycerides ≥ 250 mg/dL.

6.3. Lifestyle Restrictions**6.3.1. Meals and Dietary Restrictions**

- Refrain from consumption of red wine, Seville oranges, grapefruit or grapefruit juice, pomelos, exotic citrus fruits, grapefruit hybrids, or fruit juices from 7 days prior to each first dose of study treatment in Part A up until discharge from the unit. In Part B, subjects must refrain from consumption of red wine, Seville oranges, grapefruit or grapefruit juice, pomelos, exotic citrus fruits, grapefruit hybrids, or fruit juices from 7 days prior to the first dose of study treatment until after the final dose.

6.3.2. Caffeine, Alcohol, and Tobacco

- During each dosing period, participants will abstain from ingesting caffeine- or xanthine-containing products (e.g., coffee, tea, cola drinks, and chocolate) for 24 hours before the start of dosing until after collection of the final PK sample.
- During each dosing period, participants will abstain from alcohol for 24 hours before the start of dosing until after collection of the final PK sample.
- Use of tobacco products will not be allowed from 6 months prior to screening until after the final follow-up visit.

6.3.3. Activity

- Participants will abstain from strenuous exercise for 48 hours before each blood collection for clinical laboratory tests. Participants may participate in light recreational activities during studies (e.g., watching television, reading).
- Participants will abstain from travelling to regions of high endemic infection, as determined by the investigator, for the duration of the study.

6.4. Screen Failures

Screen failures are defined as participants who consent to participate in the clinical study but are not subsequently randomized. A minimal set of screen failure information is required to ensure transparent reporting of screen failure participants to meet the Consolidated Standards of Reporting Trials (CONSORT) publishing requirements and to respond to queries from regulatory authorities. Minimal information includes demography, screen failure details, eligibility criteria, and any SAEs.

Individuals who do not meet the criteria for participation in this study (screen failure) may be rescreened only on approval of the GSK Medical Monitor. Rescreened participants should be assigned the same participation number as for the initial screening.

7. TREATMENTS

The term study treatment is used throughout the protocol and is defined as any investigational treatment(s), marketed product(s), placebo, or medical device(s) intended to be administered to a study participant according to the study protocol.

7.1. Treatments Administered

	Study Treatment	
Product name:	GSK2982772	Placebo
Formulation description	API filled capsule	Placebo blend filled capsule
Dosage form:	HPMC capsule	HPMC capsule
Unite dose strength(s)/Dosage level(s):	120 mg maximum fill per capsule	NA
Route of administration:	For oral use only	For oral use only
Dosing instructions:	Dose with water	Dose with water
Physical description:	Size 00, white, opaque capsule containing white to almost white solid	Size 00, white, opaque capsule containing white to almost white solid
Source of procurement	Study medication is supplied by GlaxoSmithKline	Study medication is supplied by GlaxoSmithKline
Method for individualizing dosage:	Site to assemble	Site to assemble

7.2. Method of Treatment Assignment

On Day -1 or Day 1 participants will be assigned a unique number (randomization number) in ascending numerical order. The randomization number encodes the participant's assignment to either GSK2982772 or placebo, according to the randomization schedule generated prior to the study by the Statistics Department at GSK, using validated internal software.

All participants will be centrally randomized using an Interactive Voice/Web Response System (IVRS/IWRS). Before the study is initiated, the telephone number and call-in directions for the IVRS and/or the log in information & directions for the IWRS will be provided to the site.

Study treatment will be dispensed at the study visits summarized in SoA. Each participant will be dispensed blinded study treatment, labelled with his/her unique randomization number, throughout the study. Returned study treatment should not be re-dispensed to the participants

In Cohorts 1 and 2, subjects will be randomized in a 3:1 ratio to either GSK2982772 or placebo. In Cohorts 3, 4 and 5, subjects will be randomized in a 9:5 ratio to either GSK2982772 or placebo. In Cohort 1, the subjects will be randomized to one of four sequences (ABC, ABP, APC, PBC), where the treatments are:

A	120 mg TID
B	240 mg TID
C	360 mg BID
P	Placebo

The planned dose levels are defined in Section 5.1.

The randomization will reflect the fact that at least 2 of the 12 subjects in Cohorts 1 and 2 and at least 2 of the 14 subjects in Cohort 4 and 5 (one subject will receive GSK2928772 and one subject will receive matched-placebo) will be dosed first (on Day 1) in each part to enable dose staggering.

Once a treatment allocation number has been assigned to a subject, it cannot be reassigned to any other subject.

7.3. Blinding

This will be a double blind (sponsor-unblinded) study and the following will apply:

- The Investigator or treating physician will remain blinded to each participant's assigned study treatment throughout the course of the study. In order to maintain this blind, an otherwise uninvolved 3rd party will be responsible for the reconstitution and dispensation of all study treatment and will endeavour to ensure that there are no differences in time taken to dispense following randomization
- This 3rd party will instruct the participant to avoid discussing the taste, dosing frequency, or packaging of the study treatment with the investigator
- Unblinded monitors and in the event of a Quality Assurance audit, the auditor(s) will be allowed access to un-blinded study treatment records at the site(s) to verify that randomization/dispensing has been done accurately.
- The IVRS/IWRS will be programmed with blind-breaking instructions.
- In case of an emergency, the investigator has the sole responsibility for determining if unblinding of a participant's treatment assignment is warranted. Participant safety must always be the first consideration in making such a determination.
- If the investigator decides that unblinding is warranted, the investigator should make every effort to contact GSK prior to unblinding a participant's treatment assignment unless this could delay emergency treatment of the participant.
- If a participant's treatment assignment is unblinded, GSK must be notified within 24 hours after breaking the blind.
- The date and reason that the blind was broken must be recorded in the source documentation and Case Report Form (CRF), as applicable.

- A subject will be withdrawn if the subject's treatment code is unblinded by the investigator or treating physician. The primary reason for discontinuation (the event or condition which led to the unblinding) will be recorded in the CRF.
- GSK's Global Clinical Safety and Pharmacovigilance (GCSP) staff may unblind the treatment assignment for any subject with an SAE. If the SAE requires that an expedited regulatory report be sent to one or more regulatory agencies, a copy of the report, identifying the subject's treatment assignment, may be sent to investigators in accordance with local regulations and/or GSK policy.

7.4. Preparation/Handling/Storage/Accountability

- The investigator or designee must confirm appropriate temperature conditions have been maintained during transit for all study treatment received and any discrepancies are reported and resolved before use of the study treatment.
- Only participants enrolled in the study may receive study treatment and only authorized site staff may supply or administer study treatment. All study treatments must be stored in a secure, environmentally controlled, and monitored (manual or automated) area in accordance with the labeled storage conditions with access limited to the investigator and authorized site staff.
- The investigator, institution, or the head of the medical institution (where applicable) is responsible for study treatment accountability, reconciliation, and record maintenance (i.e., receipt, reconciliation, and final disposition records).
- Further guidance and information for the final disposition of unused study treatment are provided in the SRM.
- Under normal conditions of handling and administration, study treatment is not expected to pose significant safety risks to site staff.
- A Material Safety Data Sheet (MSDS)/equivalent document describing occupational hazards and recommended handling precautions either will be provided to the investigator, where this is required by local laws, or is available upon request from GSK.

7.5. Treatment Compliance

- When the individual dose for a participant is prepared from a bulk supply, the preparation of the dose will be confirmed by a second member of the study site staff.
- When participants are dosed at the site, they will receive study treatment directly from the investigator or designee, under medical supervision. The date and time of each dose administered in the clinic will be recorded in the source documents. The dose of study treatment and study participant identification will be confirmed at the time of dosing by a member of the study site staff other than the person administering the study treatment. Study site personnel will examine each participant's mouth to ensure that the study treatment was ingested.

7.6. Concomitant Therapy

Any medication or vaccine (including over-the-counter or prescription medicines, vitamins, and/or herbal supplements) that the participant is receiving at the time of enrolment or receives during the study must be recorded along with:

- reason for use
- dates of administration including start and end dates
- dosage information including dose and frequency

The Medical Monitor should be contacted if there are any questions regarding concomitant or prior therapy.

Participants must abstain from taking prescription or non-prescription drugs (including vitamins and dietary or herbal supplements) within 7 days (or 14 days if the drug is a potential enzyme inducer) or 5 half-lives (whichever is longer) before the start of study treatment until completion of the follow-up visit, unless, in the opinion of the investigator and sponsor, the medication will not interfere with the study.

Paracetamol at doses of ≤ 2 grams/day, is permitted for use any time during the study. Other concomitant medication may be considered on a case-by-case basis by the Investigator in consultation with the Medical Monitor if required.

7.7. Treatment after the End of the Study

Subjects will not receive any additional treatment from GSK, or with GSK2982772, after completion of the study because only healthy volunteers are eligible for study participation.

8. DISCONTINUATION CRITERIA

8.1. Discontinuation of Study Treatment

8.1.1. Dose Modification/Stopping Criteria

This protocol allows some alteration from the currently outlined dosing schedule, but the maximum total daily dose will not intentionally exceed the 13-week NOAEL exposure in monkeys. Currently, the highest planned dose is 720 mg/day of GSK2982772.

The decision to proceed to the next dose level of GSK2982772 in each part of this study will be made by the DEC, including the Medical Monitor and the Investigator and relevant clinical site staff (see Section 10.5) based on safety, tolerability, and preliminary PK data obtained in at least 6 subjects (through at least 24 hours post-dose) with at least 6 subjects having received active treatment (GSK2982772) at the prior dose level. The actual doses to be administered may be adjusted based on safety, tolerability and preliminary PK data at previous dose levels; these dose adjustments may involve either an increase or a decrease in the planned dose, but will not exceed the PK criteria defined in Section 8.1.2. Planned doses may also be repeated.

The Principal Investigator and the GSK Medical Monitor will review the following and dosing **will be** halted and progression to the next higher dose level stopped if:

- One (1) or more subjects experience a SAE which has a reasonable possibility of relation to study drug.
- Two (2) or more subjects experience a severe or clinically significant non-serious AE (based upon investigator judgment) which has a reasonable possibility of relation to study drug.
- Two (2) or more subjects in a Part A cohort or 3 or more subjects in a Part B cohort experience the same AE of moderate severity which has a reasonable possibility of relation to study drug.
- Consistent Common Terminology Criteria for Adverse Events (CTCAE) Nervous System AEs of any grade occur across subjects that have a reasonable possibility of relation to study drug.

If dosing is halted and if deemed acceptable by GSK internal safety review to proceed with or modify dose escalation to further characterize the safety profile, a formal request with appropriate data and substantial amendment will be submitted to MHRA (Medicines and Healthcare Products Regulatory Agency) for approval.

8.1.2. Pharmacokinetic Dose Modification or Stopping Criteria

The 240 mg TID dose and/or the 360 mg BID dose in Cohorts 1, 4 and 5 may be adjusted up or down based on PK data from previous treatment periods. It is planned that the 95th percentile for the predicted $AUC_{(0-24)}$ values will not exceed the maximum $AUC_{(0-24)}$ value observed at the NOAEL and for C_{max} the 95th percentile will not exceed the mean C_{max} at the NOAEL.

[figure not shown]
8.1.3. Liver Chemistry Stopping Criteria

Liver chemistry stopping and increased monitoring criteria have been designed to assure participant safety and evaluate liver event etiology.

Discontinuation of study treatment for abnormal liver tests is required when:

- when in the presence of abnormal liver chemistries not meeting protocol-specified stopping rules, the investigator believes study treatment discontinuation is in the best interest of the participant.

Phase I Liver Chemistry Stopping Criteria – Liver Stopping Event Algorithm

Liver Safety Required Actions and Follow up Assessments Section can be found in [Appendix 7](#).

8.1.4. QTc Stopping Criteria

A subject that meets either bulleted criterion based on the average of triplicate ECG readings will be withdrawn from study treatment.

- QTcF > 500 msec,
- Change from baseline: QTc > 60 msec
- The *same* QT correction formula *must* be used for *each individual participant* to determine eligibility for and discontinuation from the study (i.e., QTcF in this study). This formula may not be changed or substituted once the participant has been enrolled.

For example, if a participant is eligible for the protocol based on QTcF, then QTcF must be used for discontinuation of this individual participant as well.

- Once the QT correction formula has been chosen for a participant's eligibility, the *same formula* must continue to be used for that participant *for all QTc data being collected for data analysis*. Safety ECGs and other non-protocol specified ECGs are an exception.
- The QTc should be based on single or averaged QTc values of triplicate electrocardiograms obtained over a brief (e.g., 5-10 minute) recording period. If an ECG demonstrates a prolonged QTc, obtain 2 more ECGs over a brief period (5-10 minutes), and then use the averaged QTc values of the 3 ECGs to determine whether the subject should be discontinued from the study.

See the SoA for data to be collected at the time of treatment discontinuation and follow-up and for any further evaluations that need to be completed.

8.1.5. Individual Safety Stopping Criteria

- If a participant experiences a serious or severe clinically significant AE that in the clinical judgement of the Investigator, after consultation with the medical monitor, is possibly, probably or definitely related to investigational product.
- The participant becomes pregnant.
- The participant initiates treatment with any prohibited medications.
- The participant develops a serious opportunistic or atypical infection.
- If any of the liver chemistry stopping criteria (See Section 8.1.3) or QTc stopping criteria (see Section 8.1.4) are met.
- The participant experiences any signs of suicidal ideation or behaviour (See Section 9.3.6).

8.1.6. Group Safety Stopping Criteria

In addition to the criteria specified above, AEs, SAEs, laboratory abnormalities, ECG abnormalities and changes in vital signs occurring across all randomized subjects will be regulatory reviewed by the Sponsor Safety Review Team (SRT) in order to ensure appropriate subject safety. Any changes to the study due to safety reasons will be promptly communicated to the appropriate Regulatory Authorities.

8.1.7. Nervous System Stopping Criteria

The CNS observations in the 4-week GLP toxicology study in monkeys were found to be random, diverse, and unpredictable in monkeys (see Section 3.3.1). There were no similar findings observed in the 13-week GLP toxicology study in monkeys. The CTCAE Nervous System is a monitoring tool which provides the Principal Investigator the appropriate guidance for grading of a neurological event. The significance of any neurological event experienced by a subject will be determined based on clinical judgment, characteristics of the event and/or based upon changes from a baseline assessment.

The Principal Investigator and the GSK Medical Monitor will review all neurological events utilizing the CTCAE Nervous System criteria and dosing may be halted if and progression to the next higher dose level stopped as per Section 8.1.1.

A subject will be withdrawn from the study if:

- A Grade 3 or greater CTCAE Nervous System finding is observed or a significant neurologic change from a subject's baseline physical examination is observed.
- Any adverse event included in the CTCAE for Nervous System, which is also considered to be clinically significant by the Principal Investigator, will be reviewed for potential subject withdrawal.

Note: [Appendix 8](#) (Section 12.8) provides Guidance for Grading Adverse Events that is taken from the CTCAE Version 4.03.

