3.3.3. Overall Benefit:Risk Conclusion

The known risks associated with GSK2982772 can be appropriately mitigated by the careful selection of study participants and the proposed safety monitoring procedures. As such, the risk to potential subjects is considered low. Routine safety and tolerability will be evaluated from reported AEs, scheduled physical examinations, vital sign measurements, cardiac rhythm monitoring, 12-lead ECGs, and clinical laboratory test results as well as continued observation by clinical staff.

The study will be conducted in a hospital-based unit or unit with immediate access to hospital facilities for the treatment of medical emergencies. The in-house periods as detailed in the SoA (Section 2) will allow for continuous medical monitoring for all subjects following the first dose in each treatment group. Subjects will only be discharged from the unit 48 hours post-dose if the Investigator deems it safe to do so.

Taking into account the measures taken to minimize risk to subjects participating in this study, the potential risks identified in association with GSK2982772 are justified by the anticipated benefits that may be afforded by the future development of a new therapy in an area of unmet need.

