9.1. Adverse Events

The definitions of an AE or SAE can be found in [Appendix 4](#).

The investigator and any designees are responsible for detecting, documenting, and reporting events that meet the definition of an AE or SAE and remain responsible for following up AEs that are serious, considered related to the study treatment or the study, or that caused the participant to discontinue the study treatment (see Section 8).

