9.3.2. Neurological Exams

Neurological examination will include, at a minimum, assessment of: mental status, gait, balance, coordination, cranial nerves, motor power, reflexes, and sensory system (light touch and pain). Assessments will be standardized across all scheduled time points (see SoA). Significant changes from the baseline or any clinically significant changes will be noted as part of further scheduled examinations or unscheduled examinations (if needed).

Clinically significant abnormalities or changes in status from baseline will be:

- entered as an adverse event,
- may trigger increased monitoring of the subject(s),
- may result in withdrawal of the subject (see Section 8.2),
- may result in referral to a specialist.

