- The investigator is obligated to perform or arrange for the conduct of supplemental measurements and/or evaluations as medically indicated or as requested by GSK to elucidate the nature and/or causality of the AE or SAE as fully as possible. This may include additional laboratory tests or investigations, histopathological examinations, or consultation with other health care professionals.
- If a participant dies during participation in the study or during a recognized follow-up period, the investigator will provide GSK with a copy of any post-mortem findings including histopathology.
- New or updated information will be recorded in the originally completed CRF.
- The investigator will submit any updated SAE data to GSK within 24 hours of receipt of the information.

Reporting of SAE to GSK

SAE Reporting to GSK via Paper CRF

- Email transmission of the SAE paper CRF is the preferred method to transmit this information to the medical monitor or the SAE coordinator.
- In rare circumstances and in the absence of email equipment, notification by telephone is acceptable with a copy of the SAE data collection tool sent by overnight mail or courier service.
- Initial notification via telephone does not replace the need for the investigator to complete and sign the SAE CRF pages within the designated reporting time frames.
- Contacts for SAE reporting can be found in Study Reference Manual.

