10.7. Appendix 7: Reporting Standards for Missing Data

10.7.1. Premature Withdrawals

Element	Reporting Detail
General	 Participant study completion (i.e. as specified in the protocol) was defined as one who has completed all phases of the study including the last scheduled procedure shown in the SoA (see Appendix 2). Withdrawn participants may be replaced in the study. Additional replacement participants may be randomized to guarantee that sufficient participants are treated with GSK2982772 at any given dose before escalating to the following dose. Replacement participants will be assigned to the same treatment sequence (Cohort 1) or treatment (Cohorts 2-5) but have different subject numbers and randomisation numbers assigned. All available data from participants who were withdrawn from the study will be listed and all available planned data will be included in summary tables and figures, unless otherwise specified.
Liver Chemistry Stopping Criteria	 Discontinuation of study treatment for abnormal liver tests is required when: in the presence of abnormal liver chemistries not meeting protocol-specified stopping rules, the investigator believes study treatment discontinuation is in the best interest of the participant. ALT ≥ 3 x ULN. Note: Refer to Appendix 7 of the protocol for details of the required assessments if a participant meets the above criteria.
QTc Stopping Criteria	 A participant that meets either bulleted criterion based on the average of triplicate ECG readings will be withdrawn from study treatment: QTcF > 500 msec Change from baseline: QTcF > 60 msec
Nervous System Stopping Criteria	 A participant will be withdrawn from the study if: A Grade 3 or greater CTCAE Nervous System finding is observed or a significant neurologic change from a participant's baseline physical examination is observed. Any adverse event included in the CTCAE for Nervous System, which is also considered to be clinically significant by the Principal Investigator, will be reviewed for potential participant withdrawal.

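### Protocol 8.1.7 withdraws nervous-system cases from the study, not just from treatment; read literally, no neurological examination at a fixed time follows the event

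*Protocol*

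**What the plan says.** Protocol 8.1 covers stopping study treatment; leaving the study has its own section, 8.2. Section 8.1.7 stands under 8.1, but its list is introduced by "A subject will be withdrawn from the study if". The first bullet is automatic: a CTCAE nervous-system finding of Grade 3 or higher, or a significant neurological change from the subject's baseline. The second bullet only calls for a review of other clinically significant nervous-system events. The nervous-system row of SAP 10.7.1 carries the same rule: "A participant will be withdrawn from the study if". Protocol 9.3.2 says that neurological changes may lead to withdrawal and points to 8.2.

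The QTc rule is mostly worded the other way. In 8.1.4, a subject meeting a criterion "based on the average of triplicate ECG readings will be withdrawn from study treatment". The last bullet of that section then tells the site to "use the averaged QTc values of the 3 ECGs to determine whether the subject should be discontinued from the study".

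Section 8.2 refers to the schedule of activities for data at discontinuation and follow-up. Its instruction to make every effort to complete the follow-up assessments is worded for a subject who chooses to leave, not for one who is withdrawn.

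**The concern.** Safety is the primary objective, and CNS effects are the first risk listed in protocol 3.3.1. Stopping the drug is what protects the volunteer. Ending participation adds no protection beyond withholding later doses; mainly, it ends measurement. This is plainest when the doses are already in, after the last dose of a Part A period or on Day 16 of Part B.

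What would lapse is the standardised neurological examination together with scheduled ECGs, vital signs and laboratory tests, which are primary endpoints. The dose escalation review in 10.5 covers Part B data through Day 16, so literal withdrawal would also shorten the record available for that case.

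The trigger need not be exotic. The first bullet of 8.1.7 requires no link to study drug. In the grading table in Appendix 8, syncope exists only at Grade 3 and vasovagal reaction starts at Grade 3. That table is guidance to be weighed by the investigator, but a simple faint can meet the wording.

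**Working it through.** No sample size or error rate is involved. The check compares wording and counts scheduled examinations.

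**1. What each stopping rule ends**

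| Trigger | Protocol | SAP 10.7.1 |
|---|---|---|
| Liver | treatment (8.1.3) | treatment |
| QTc | treatment in the operative sentence, study in the last bullet (8.1.4) | treatment |
| Suicidality | study medication (9.3.6) | no row |
| Nervous system | study (8.1.7) | study |

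The plan uses both terms and applies the wider one to nervous-system cases. The conflict with the parent heading exists only in the protocol, because the SAP section is headed as dealing with premature withdrawals.

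**2. Part B neurological examinations**

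These are read from the schedule in SAP 10.2.1.2, because the protocol's Part B table is cut off in the text available. Examination days are 1, 2, 3, 7 and 16, with none on Day 17 or at follow-up. Days lost = examination days later than the stop day.

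| Stop day | Days lost | Scheduled after the event if withdrawn |
|---|---|---|
| 1 | 4 (2, 3, 7, 16) | 0 |
| 2 | 3 (3, 7, 16) | 0 |
| 3 to 6 | 2 (7, 16) | 0 |
| 7 to 14 | 1 (16) | 0 |

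The Day 17 full physical, which includes the neurological system (9.3.1), would lapse too. The Part B follow-up has a brief physical, whose minimum content has no neurological component.

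**3. Part A neurological examinations (protocol 2.1), in hours after the first dose**

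- TID: doses at 0, 7 and 14. Examinations at 2, 9, 16, 24 and 48, plus 14 + 24 = 38 and 14 + 48 = 62. An event found at 16 h loses four: 24, 38, 48 and 62.
- BID: doses at 0 and 12. Examinations at 2, 14, 24 and 48, plus 12 + 24 = 36 and 12 + 48 = 60. An event found at 14 h loses four: 24, 36, 48 and 60.
- No neurological examination is scheduled at follow-up.

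**4. Which repair works**

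- Keeping only the calendar of neurological examinations leaves a wait of up to 16 − 7 = 9 days. An event first found on Day 16 has only the Day 17 full physical after it.
- Keeping every remaining assessment would be heavy. Vital signs are daily, so a Day 5 stop means 17 − 5 = 12 further dates.
- Anchoring to the event gives three dated examinations after discontinuation (24 h, 48 h, follow-up) for a stop on Days 1 to 14, and one (follow-up) for an event first found on Day 16. With a half-life of 2 to 3 h (5.7), 48 h is 48/3 = 16 to 48/2 = 24 half-lives, so the anchor covers washout.

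**The case against.** The strongest reply is that the literal reading is not how a unit would act, and that other provisions already cover the case:

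- Section 9.1 makes the investigator responsible for following events that are serious, related, "or that caused the participant to discontinue the study treatment".
- Section 9.1.3 follows serious events and events of special interest to resolution or stabilisation, and points to 3.3.1, where CNS effects come first.
- Appendix 4 adds: "The investigator is obligated to perform or arrange for the conduct of supplemental measurements and/or evaluations as medically indicated or as requested by GSK".
- Section 9.3.2 foresees further scheduled or unscheduled examinations.
- The synopsis allows additional follow-up visits, and a note in both schedules allows extra examinations or turning a brief physical into a full one.
- Section 3.3.3 states: "Subjects will only be discharged from the unit 48 hours post-dose if the Investigator deems it safe to do so".

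All of this stands, and it rules out the reading that a volunteer with a serious neurological event would go unexamined. None of these provisions names a neurological examination at a set time after the event.

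It is also true that no SAP display uses neurological examinations by time point, that the examination is not itself a listed primary endpoint, and that significant changes are captured as adverse events whether or not the participant stays in. The lost examinations therefore do not bias any planned summary of that examination. The loss is in the standardised record of the individual case, and in the scheduled ECG, vital-sign and laboratory data that the summaries do use.

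Finally, a note in SAP 5.1 shows that the SAP postdates Cohort 4, so changing it cannot alter care already given. That is right; the SAP edit is for consistency.

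**Conclusion.** The point holds as a wording fault with a practical consequence. A rule placed under treatment discontinuation ends study participation and, followed as written, leaves zero scheduled neurological examinations after the event at any stop day. The size is one to four examination days lost per Part B case stopping on Days 1 to 14, and four examinations lost for a Part A event found 2 h after the last dose. The documents give no basis for saying how many such cases to expect.

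This rests on two assumptions: that the site applies 8.1.7 literally, and that the SAP's copy of the Part B schedule matches the protocol's.

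A reader might infer three stronger things that the documents do not support:

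- That neurological follow-up is absent. The event-driven duties remain.
- That every nervous-system event forces withdrawal. Only the first bullet of 8.1.7 does.
- That QTc cases are also removed from the study. The operative sentence of 8.1.4 and the SAP row both say treatment, so the last bullet is a slip.

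This is a cheap improvement, not a flaw in the primary analysis.

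**What to change.** 1. In protocol 8.1.7, and in the matching SAP 10.7.1 row, replace withdrawal from the study with withdrawal from study treatment. State that the participant stays in the study for safety follow-up unless consent is withdrawn.
2. In 8.1.7, require the existing neurological examination at discontinuation, at 24 and 48 h after the last dose while inpatient, and at the existing follow-up visit. An event first found after dosing has ended gets the follow-up examination.
3. In 8.2, extend the sentence on completing follow-up assessments to a subject who withdraws or is withdrawn.
4. As a tidy-up only, say study treatment in the last bullet of 8.1.4.

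Leave the triggers and the adverse-event follow-up rules as they are. An added Part A follow-up ECG and conforming edits to the replacement rules or the C-SSRS note are not essential.

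The cost is wording in three protocol sections and one SAP row. A Part B case has up to three dated examinations after the one at discontinuation, with no new visit if the participant stays in the unit to 48 h after the last dose. In Part A, where 24 and 48 h after the last dose are already scheduled, the addition after discontinuation is one follow-up examination.
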